#### 9.3.2 Evaluation of non-target lesions

Complete Response (CR): Disappearance of all non-target lesions and normalization of tumor marker level

Incomplete Response/  
Stable Disease (SD): Persistence of one or more non-target lesion(s) and/or maintenance of tumor marker level above the normal limits

Progressive Disease (PD): Appearance of one or more new lesions and/or unequivocal progression of existing non-target lesions

Although a clear progression of "non-target" lesions only is exceptional, in such circumstances the opinion of the treating physician should prevail, and the progression status should be confirmed at a later time by the review panel (or study chair).

#### 9.3.3 Evaluation of best overall response

The best overall response is the best response recorded from the start of the treatment until disease progression/recurrence (taking as reference for progressive disease the smallest measurements recorded since the treatment started). The patient's best response assignment will depend on the achievement of both measurement and confirmation criteria (see section 9.3.1).

Target Lesions	Non-Target Lesions	New Lesions	Overall Response
CR	CR	No	CR

CR	Incomplete response/SD	No	PR
PR	Non-PD	No	PR
SD	Non-PD	No	SD
PD	Any	Yes or No	PD
Any	PD	Yes or No	PD
Any	Any	Yes	PD

**Note:**

- 1) Patients with a global deterioration of health status requiring discontinuation of treatment without objective evidence of disease progression at that time should be classified as having "symptomatic deterioration."
- 2) In some circumstances, it may be difficult to distinguish residual disease from normal tissue. When the evaluation of complete response depends on this determination, it is recommended that the residual lesion be investigated (fine needle aspirate/biopsy) before confirming the complete response status.

#### **9.4 Confirmatory Measurement/Duration of Response**

##### **9.4.1 Confirmation**

To be assigned a status of PR or CR, changes in tumor measurements must be confirmed by repeat assessments that should be performed 4 weeks after the criteria for response are first met. In the case of SD, follow-up measurements must have met the SD criteria at least once after study entry at a minimum interval of 9 weeks (see section 9.3.3).

##### **9.4.2 Duration of overall response**

The duration of overall response is measured from the time measurement criteria are met for CR or PR (whichever is first recorded) until the first date that recurrent or progressive disease is objectively documented (taking as reference for progressive disease the smallest measurements recorded since the treatment started).

The duration of overall CR is measured from the time measurement criteria are first met for CR until the first date that recurrent disease is objectively documented.

##### **9.4.3 Duration of Stable Disease**

Stable disease is measured from the start of the treatment until the criteria for progression are met, taking as reference the smallest measurements recorded since the treatment started.

#### **9.5 Progression-Free Survival**

Progression-free survival (PFS) is defined as the duration of time from start of treatment to time of progression or death, whichever occurs first.

## 10. REGULATORY AND REPORTING REQUIREMENTS

### 10.1 Expedited Adverse Event Reporting

The PI of this study has primary responsibility for the overall study, including patient welfare, data integrity, and monitoring of adverse events. Adverse event lists, guidelines, and instructions for AE reporting can be found in Section 7.0 (Adverse Events: List and Reporting Requirements).

### 10.2 Data Reporting

#### 10.2.1 Institutional Review Board

The protocol, the proposed informed consent, and all forms of participant information related to the study (e.g. advertisements used to recruit participants) will be reviewed and approved by the IRB and Moffitt Cancer Centers' Scientific Review Committee (SRC). Any changes made to the protocol will be submitted as a modification and will be approved by the IRB prior to implementation. The Protocol Director will disseminate the protocol amendment information to all participating investigators. No subject is to be enrolled on this protocol until the Center's Institution Review Board has approved it.

#### 10.2.2 Data Reporting

Moffitt Cancer Center's Data and Safety Monitoring Committee (DSMC) will be the monitoring entity for this study. The DSMC will audit study-related activities to determine whether the study has been conducted in accordance with the protocol, local standard operating procedures, FDA regulations, and Good Clinical Practice (GCP). In addition, the DSMC will regularly review serious adverse events and protocol deviations associated with the research to ensure the protection of human subjects. Results of the DSMC audit will be communicated to the IRB and the appropriate regulatory authorities at the time of continuing review, or in an expedited fashion, as needed.

Data will be captured in Oncore, Moffitt's Clinical Trials Database. Regulatory documents and case report forms will be monitored internally according to Moffitt Cancer Center Monitoring Policies. Monitoring will be performed regularly to verify data is accurate, complete, and verifiable from source documents; and the conduct of the trial is in compliance with the currently approved protocol/amendments, Good Clinical Practice (GCP), and applicable regulatory requirements.

#### 10.2.3 Informed Consent

The investigator is responsible for patient care and for obtaining consent by the patient. Written informed consent must be obtained prior to entry of any patient.

#### 10.2.4 Hospital/Clinic Records

Hospital records for patients on this study are the responsibility of the investigator. They will be available for review by the sponsors of the trial, health care personnel involved in this study, the IRB, DHHS, and the FDA.

#### 10.2.5 Investigator Study Files

The Principal Investigator is responsible for maintaining study files for a period of 2 years following the date a marketing application is approved for the drug for the indication for which it is being investigated; or if no application is to be filed or if the application is not approved for such indication, until 2 years after the investigation is discontinued and FDA is notified. The following documents should be kept in the study files:

A completed, signed FDA Form 1572 (Statement of Investigator) and copies of all current curricula vitae of all sub investigators listed on the Statement of the Investigator.

- The original protocol and all amendments
- Final IRB approval, annual renewals and all IRB correspondence
- Blank Case Report Forms
- Copy of all IRB approved Informed Consent forms with applicable version date
- Updated laboratory certification and laboratory values (covering entire time of study)
- Copy of all patient's signed informed consent forms
- The final completed case report form for all patients

#### **10.2.6 Data Management Plan**

Electronic case report forms for specified protocol related information on each trial patient, using the Oncore system, will be created. Electronic data will be kept secure within the Oncore password protected system. Paper copies of the documentation from the medical record which support the data entered into Oncore will be kept in patient specific binders in a secure, locked, and HIPPA compliant environment.

### **10.3 Reporting and Exclusions**

#### Evaluation of Toxicity

All patients will be evaluable for toxicity from the time of their first treatment with 5-FU/capecitabine and IFN alpha-2b. Adverse events that occur during screening will not be captured. Adverse events will only be captured until 30 days after the last dose of any investigational drug.

## **11. STATISTICAL CONSIDERATIONS**

### **11.1 Study Endpoints**

#### 11.1.1 Primary Objective

To establish the objective response rate to IFN alpha-2b and 5-FU/capecitabine using RECIST criteria in patients with unresectable/metastatic CSCC after 3 cycles of treatment (9 weeks).

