## 1. OBJECTIVES

### 1.1 Primary Objective(s)

To establish the objective response rate, using RECIST criteria, to the combination Treatment of Interferon alpha-2b and 5-FU/Capecitabine in patients with unresectable and/or metastatic cutaneous squamous cell carcinoma of the skin

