## 9. MEASUREMENT OF EFFECT

### Antitumor Effect – Solid Tumors

For the purposes of this study, patients should be re-evaluated for response every nine weeks.

If treatment is held for adverse event recovery thereby extending cycle length, then imaging and tumor measurement intervals may be correspondingly altered so that the patient is imaged every third cycle.

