### **11.2 Statistical Design**

This is a single arm, Phase II trial using a Simon's two-stage design to evaluate the RECIST response rate to 5-FU/capecitabine and interferon alpha-2b in patients with

unresectable or metastatic squamous cell carcinoma of the skin after 3 cycles of treatment. Patients must have received at least one cycle of 5-FU/capecitabine and PEG-IFN

alpha in order to be evaluable for response. We wish to distinguish between a response rate of 10%, which would be uninteresting, and a response rate of >30%, which would merit further testing. Choosing an alpha type error probability of 0.1 and a beta type error probability of 0.1 would mean that in order to proceed beyond the first stage, at least 2 of first 16 patients would have to have responses, and at least 5 of

25 patients (statistics based on 25 evaluateable patients with a total enrollment of 30 patients) would have to respond in order declare this a regimen of interest.

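### Does the plan leave open whether a response first seen after the cycle-3 assessment counts toward the 2-of-16 and 5-of-25 cutoffs?

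*Combined protocol and SAP*

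**What the plan says.** Section 1.1 states the primary objective without a time point: "To establish the objective response rate, using RECIST criteria, to the combination". Section 11.1.1 adds one, placing the response rate "in patients with unresectable/metastatic CSCC after 3 cycles of treatment (9 weeks"). Section 11.2 introduces the Simon design as an evaluation of the RECIST response rate in "unresectable or metastatic squamous cell carcinoma of the skin after 3 cycles of treatment", and the same paragraph gives the decision rule: "at least 2 of first 16 patients would have to have responses, and at least 5 of" 25 at the end.

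Section 9 supplies the measurement rules. It says "patients should be re-evaluated for response every nine weeks", with imaging at every third cycle if treatment is held. Section 9.3.3 says "The best overall response is the best response recorded from the start of the treatment until disease progression/recurrence". Section 9.4.1 requires that "changes in tumor measurements must be confirmed by repeat assessments that should be performed 4 weeks after the criteria for response are first met". Section 9.4.2 says that duration of response "is measured from the time measurement criteria are met for CR or PR (whichever is first recorded"). Section 4.4 allows up to 9 cycles, which is 27 weeks at 21 days each.

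**The concern.** Assessments at nine-week intervals over 9 cycles fall at about weeks 9, 18 and 27. A confirmed partial response first seen at week 18 qualifies as a best overall response under 9.3.3, but it is not a response after 3 cycles under 11.1.1. Section 11.2 speaks only of patients having responses and does not repeat the window or the confirmation rule next to the cutoffs. It also does not say when stage 1 is judged.

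The cutoffs are small counts, so one patient can matter. A count one below a cutoff, plus one late responder, turns a stop into a continuation or a negative trial into a positive one. The quoted error rates hold for one fixed definition of response. If the window were chosen after the responses were known, those rates would no longer describe the procedure. The window also determines how long one waits for the 16th patient's status.

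**Working it through.** **1. The plan's own figures.** Inputs from Section 11.2: null rate 10%, target rate 30%, both error probabilities 0.1, continue with at least 2 of 16, declare with at least 5 of 25. Let X1 ~ Bin(16, p) be the stage 1 count and X2 ~ Bin(9, p) the count in the remaining 25 − 16 = 9 patients.

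P(declare) = Σ over x = 2, 3, 4 of P(X1 = x) · P(X2 ≥ 5 − x), plus P(X1 ≥ 5).

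| Term | p = 0.10 | p = 0.30 |
|---|---|---|
| x = 2 | 0.2745 × 0.0530 = 0.0145 | 0.0732 × 0.5372 = 0.0393 |
| x = 3 | 0.1423 × 0.2252 = 0.0321 | 0.1465 × 0.8040 = 0.1178 |
| x = 4 | 0.0514 × 0.6126 = 0.0315 | 0.2040 × 0.9596 = 0.1958 |
| x ≥ 5 | 0.0170 | 0.5501 |
| **P(declare)** | **0.0951** | **0.9030** |

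Both meet the stated limits. The calculation takes a response probability and does not ask which window produced it. The design is therefore correct for whichever single rate the 10% and 30% describe.

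**2. Which rate that is.** Read the sections side by side.

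- 11.2 states the design and its cutoffs in one paragraph, and the sentence that introduces the design says after 3 cycles.
- 11.1.1 says the same and adds 9 weeks.
- 1.1 is silent on timing, so it contradicts neither.
- 9.3.3 defines a standard RECIST quantity and does not name it as the primary endpoint.
- Section 11 does not mention best overall response.

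The specific statistical section governs the test, and Section 9 supplies general definitions.

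**3. Whether that reading works with confirmation.** A response first met at week 9 is confirmed at about week 9 + 4 = 13. Section 9.4.2 dates a response from when the measurement criteria are met, so this patient is a week-9 responder whose status becomes known at week 13. The confirmation visit is an added assessment that 9.4.1 already requires, so it does not conflict with nine-weekly imaging.

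**4. How often one patient could matter.** The probability of finishing exactly one short of a cutoff is P(X1 = 1) + P(X1 ≥ 2 and X1 + X2 = 4).

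- At p = 0.10: 0.3294 + 0.1223 = 0.452.
- At p = 0.30: 0.0228 + 0.0506 = 0.073.

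These values hold for this design under any definition of response. They add two events with different consequences, and a change of decision also needs a late responder.

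**5. What a different window would do.** The documents give no share of late responses, so these are assumptions.

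| Assumption | Rate counted | P(declare) |
|---|---|---|
| Week-9 null 10%, late responses add 1 point | 0.11 | 0.129 |
| add 2 points | 0.12 | 0.169 |
| add 5 points | 0.15 | 0.310 |
| Best overall rate 30%, 90% of responses seen by week 9 | 0.27 | 0.837 |
| 80% seen by week 9 | 0.24 | 0.742 |
| 70% seen by week 9 | 0.21 | 0.617 |

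The first three rows apply if 10% was meant for week 9 and later responses are counted. The last three apply if 30% was meant for best overall response and only week-9 responses are counted. The two possible mismatches push in opposite directions.

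**The case for a change.** The best case for a change is that nothing in the plan gives Section 11 precedence over Section 9, and nothing expressly excludes a later response. After 3 cycles could mean at that assessment or from it onward. Confirmation cannot be complete at week 9, so a strictly literal nine-week cutoff does not work. There is also little slack: type I error passes 0.10 once the countable null rate exceeds 10.15%. In a single-arm trial, the event being counted is best fixed in advance.

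Part of this stands. The exclusion is implied rather than written, and one sentence would remove the doubt at no cost.

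The rest does not lead to a change. Confirmation at week 13 verifies a week-9 response and does not move it to another window. The 10.15% figure shows only that the test is calibrated near 10%; it does not show that the null rate is higher. The timing argument has a similar weakness. One can set week 13 against week 27 + 4 = 31, but week 31 is not a limit in the documents. Section 9.3.3 runs to progression, and Section 4.5 follows patients for up to a year after removal from study. Waiting matters only if fewer than 2 responses have been seen by then. Finally, the Section 8 calendar as it can be read marks tumour assessment only before the study, but that table came through PDF extraction, and Section 9 plainly requires assessment every nine weeks.

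**Conclusion.** The plan is sound as written. A responder is a patient whose complete or partial response is met at the cycle-3 assessment and confirmed under 9.4.1. Stage 1 can be judged once the 16th evaluable patient's confirmation status is known, about week 13 if treatment is not held. On that basis the design has type I error 0.0951 and power 0.9030, and no stated number, cutoff or analysis is shown to be wrong.

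The choice between a cycle-3 rate and best overall response is a fair trade-off. The first gives an early and uniform reading; the second credits late responders but delays the stage 1 decision. Late responses remain visible in the best overall response that Section 9.3.3 already defines.

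The conclusion rests on reading Section 11 as governing the test and on taking the 10% and 30% to describe the rate named in the same paragraph. If the rates were meant for best overall response, the size of the mismatch would depend on a share of late responses that the documents do not give.

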#### 11.1.2 Secondary Objective

To establish the progression free survival (PFS), overall survival (OS), and safety profile (AEs) of the combination of IFN alpha-2b and 5-FU/capecitabine in this patient population at 6 months and 1 year.

### **11.2 Statistical Design**

This is a single arm, Phase II trial using a Simon's two-stage design to evaluate the RECIST response rate to 5-FU/capecitabine and interferon alpha-2b in patients with

unresectable or metastatic squamous cell carcinoma of the skin after 3 cycles of treatment. Patients must have received at least one cycle of 5-FU/capecitabine and PEG-IFN

alpha in order to be evaluable for response. We wish to distinguish between a response rate of 10%, which would be uninteresting, and a response rate of >30%, which would merit further testing. Choosing an alpha type error probability of 0.1 and a beta type error probability of 0.1 would mean that in order to proceed beyond the first stage, at least 2 of first 16 patients would have to have responses, and at least 5 of

25 patients (statistics based on 25 evaluateable patients with a total enrollment of 30 patients) would have to respond in order declare this a regimen of interest.

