#### 11.3 Sample Size/Accrual Rate

We anticipate enrolling 1 patient every 1-2 two months for approximately 6-12 patients per year. We would like to enroll a total of 30 evaluable patients on trial for robust statistical analysis and to allow for a 20% drop out rate. Enrollment would occur over a three-year period to achieve the enrollment goals.

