#### 11.4 Analysis of Secondary Endpoints

Overall survival (OS) (the time from registration to death or date of last contact) and progression free survival (PFS) (patients alive without RECIST progression) are secondary objectives of the study. Kaplan-Meier estimates of overall and progression-free survival rates will be calculated, along with their corresponding 95% confidence intervals. The median, 6-month and 12-month overall and progression free survival rates will be estimated. Adverse events will be collected according the study calendar and tabulated for cumulative evaluation.

[REDACTED]

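### The response denominator drops treated patients who stop before completing one cycle, which biases the primary response rate and the go/no-go rules upward

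*Combined protocol and SAP*

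**What the plan says.** Section 11.2 (Statistical Design) sets a minimum exposure for the primary endpoint: "Patients must have received at least one cycle of 5-FU/capecitabine and PEG-IFN" alpha, or the patient is not evaluable for response. The same section sets a Simon two-stage rule with a null rate of 10%, a target above 30%, and alpha and beta of 0.1. The trial continues with at least 2 responses in the first 16 patients and declares interest with at least 5 in 25. The basis is given as "statistics based on 25 evaluateable patients with a total enrollment of 30 patients".

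The primary objective in section 11.1.1 sets no such minimum. It asks for the response rate "using RECIST criteria in patients with unresectable/metastatic CSCC after 3 cycles of treatment (9 weeks").

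Three other provisions matter:

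- Timing: in section 9, "patients should be re-evaluated for response every nine weeks", and for a partial or complete response section 9.4.1 adds this condition: "changes in tumor measurements must be confirmed by repeat assessments that should be performed 4 weeks after the criteria for response are first met".
- Other endpoints: PFS in section 9.5 is "the duration of time from start of treatment to time of progression or death", OS in section 11.4 is "the time from registration to death or date of last contact", and section 10.3 evaluates toxicity in all patients from first treatment. None of these requires a completed cycle.
- Sample size: section 11.3 says "We would like to enroll a total of 30 evaluable patients on trial", which does not agree with 25 evaluable of 30 enrolled in section 11.2.

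**The concern.** Whether a patient is evaluable depends on what happens after treatment starts. Sections 3.5 and 4.4 list the reasons for stopping, among them progression, intercurrent illness and unacceptable toxicity. A cycle lasts 21 days. A patient who stops within it has no scheduled response assessment, since the first is at week 9, and no confirmed response before about week 13 (9 + 4). Such patients are therefore almost all non-responders, and taking them out of the denominator moves the rate in one direction only. The early failures still count in PFS, OS and toxicity. Only the primary endpoint, and the decision built on it, loses them.

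In a single-arm trial the go/no-go rests entirely on comparing this proportion with fixed rates. A denominator selected on early outcome makes the regimen look better than it is in the population named in the objective. It also raises the chance of declaring interest if the 10% refers to that population.

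**Working it through.** **Inputs.** From section 11.2: p0 = 0.10, p1 = 0.30, continue if at least 2/16, declare if at least 5/25. The share *f* of treated patients removed is not in the documents. It is assumed and shown as a range.

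**1. The plan's own design.** With X responses in the first 16 and Y in the next 9,

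P(declare | p) = Σ (x = 2 to 16) P(X = x; 16, p) × P(Y ≥ max(0, 5 − x); 9, p).

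This gives 0.0951 at p = 0.10 and 0.9030 at p = 0.30. The probability of passing stage 1 at p = 0.10 is 0.485. The stated design reproduces and meets its error limits. The question is only which patients it is applied to.

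**2. Effect of removal on the null rate.** Suppose the true rate in all treated patients is 10% and the removed patients are all non-responders. The rate among evaluable patients is then p_eval = 0.10/(1 − f). If the removed patients would have responded at half the null rate, p_eval = (0.10 − 0.05f)/(1 − f). Putting these into the formula in step 1:

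| f | p_eval, none respond | P(pass stage 1) | P(declare) | P(declare), removed respond at 5% |
|---|---|---|---|---|
| 0 | 0.1000 | 0.485 | 0.095 | 0.095 |
| 1/30 (3.3%) | 0.1034 | 0.504 | 0.106 | 0.101 |
| 5% | 0.1053 | 0.514 | 0.112 | 0.104 |
| 10% | 0.1111 | 0.544 | 0.133 | 0.113 |

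With non-responders only, P(declare) reaches 0.10 at f = 0.015. That threshold is low because the attained alpha of 0.095 is already close to 0.10.

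**3. Limit of 30 treated patients.** Let the number evaluable be Binomial(30, 1 − f), use at most 25, and keep the cut at 5. The figures for 3.3%, 5% and 10% become 0.106, 0.112 and 0.132, so the cap hardly matters in this range.

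**4. Hypothetical upper bound.** If all five patients beyond 25 were treated cycle-1 stoppers, f = 5/30 = 16.7%. P(declare) is then 0.154 with 30 treated, or 0.169 if 25 evaluable are always reached. Thirty treated would yield 25 evaluable with probability only 0.616 at that f. No text says losses of this kind are expected.

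**5. Effect on the reported rate.** Five responses in 25 is 20.0%. Restoring one excluded patient gives 5/26 = 19.2%, and restoring three gives 5/28 = 17.9%.

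**6. The 25-versus-30 wording.** If 30 evaluable patients were analysed with the cut left at 5 (at least 2/16, then at least 5/30), alpha would be 0.159 and power 0.954. The plan does not propose this rule. The figure shows why the decision denominator has to be stated once.

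**The case against.** The strongest reply is that the 10% and 30% follow directly after the evaluability sentence and the 25 are expressly evaluable, so both rates may have been meant for evaluable patients. Alpha is then 0.095 and power 0.903, and no error rate is breached. This stands: the inflation in the table is conditional on the 10% referring to all treated patients. It does not remove the mismatch with the objective, because the estimate would then describe only patients who got through a cycle.

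It can also be said that the objective speaks of response after 3 cycles, so a one-cycle minimum is looser than the objective itself. The bracketed nine weeks makes this read as a time point, not an exposure condition.

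The stage-1 rule says only the first 16 patients, without repeating that they are evaluable. That is correct. The evaluable denominator there is inferred from the preceding sentence and from the 16 being part of the 25.

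The group is probably small. Entry requires a life expectancy over 3 months and ECOG 2 or better, and grade 3–4 toxicity attributed to treatment leads first to a hold of up to 3 weeks. What counts as having received one cycle is also not defined, and a lenient reading would shrink the group further. These points limit the size of the bias but not its direction, and an undefined criterion for entering the primary analysis needs fixing in any case.

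Finally, the 30 evaluable in section 11.3 may be loose wording for 30 enrolled (25 × 1.2 = 30). That is plausible, and the main point does not depend on it.

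**Conclusion.** The concern holds. Section 11.2 conditions the primary response rate and the 5/25 rule, and by inference the 2/16 rule, on a post-treatment event tied to non-response. No visible text restores the excluded patients as non-responders. The bias is upward.

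Its likely size is modest. With 1 to 3 of 30 treated patients removed and a true all-treated rate of 10%, the chance of declaring interest is about 0.106 to 0.133 against the stated limit of 0.10. It is 0.101 to 0.113 if the removed patients respond at half the null rate. The reported rate at the minimum success result would be overstated by roughly one to two percentage points.

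The error-rate statement assumes that the 10% null is for all treated patients. If it is for evaluable patients, alpha is kept, and the defect is that the estimate does not answer the objective in section 11.1.1. Patients who never start treatment do not cause this bias.

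**What to change.** Replace the evaluability sentence in section 11.2 with:

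> All patients who receive any dose of study treatment are included in the response denominator; those without a confirmed response, including those with no post-baseline assessment, count as non-responders. Only patients who never start treatment are replaced.

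Then:

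- Apply 2/16 and 5/25 to the first 16 and first 25 treated patients.
- State that treated patients beyond 25 contribute to estimation only, not to the decision.
- Reconcile the 30 evaluable in section 11.3 with the 25 evaluable of 30 enrolled in section 11.2.
- Report the at-least-one-cycle set as a sensitivity analysis, with receipt of one cycle defined.

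The cost is two sentences in section 11.2 and one correction in section 11.3, with no extra patients or procedures. If 10% and 30% refer to treated patients, alpha is 0.095 and power 0.903. The downside is a slightly lower reported rate. If the 30% target was meant only for patients who received one cycle, the all-treated rate is 0.30 × (1 − f) and power falls to 0.884 (3.3% early stoppers, rate 0.290), 0.873 (5%, rate 0.285) or 0.837 (10%, rate 0.270). The sponsor should therefore also state which population the 10% and 30% describe.
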